**3) Inclusion and Exclusion Criteria\***

INCLUSION CRITERIA:

- a. >18y of age,
- b. Subject or proxy who can provide informed consent
- c. Positive SARS COV2 by PCR or as determined by clinical team

EXCLUSION CRITERIA:

- a. Adults or Proxy unable to consent
- b. Individuals who are not yet adults (infants, children, teenagers)
- c. Pregnant women
- d. Prisoners
- e. Patients expected to die within 24 hours or with a “do not resuscitate” order,
- f. Multi-organ failure,
- g. History of hypersensitivity or allergy to any component of the study drug,
- h. Ongoing massive surgical or unexplained bleeding,
- i. History of bleeding or clotting disorder,
- j. Severe traumatic brain injury (Glasgow Coma Scale <6),
- k. Spinal or multiple-trauma,
- l. Cancer (incurable/terminal phase) and/or patients receiving palliative care,
- m. Enrollment in another concurrent clinical interventional study
  - if considered interfering with this study objectives
- n. Per study team discretion, any condition(s) that may prevent safe treatment, preclude adequate evaluation or adding further risk to their underlying illness.

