**5) Study-Wide Recruitment Methods\***

Potential subjects will be recruited as inpatients under the care of an attending which may include the PI or Sub-Is on this study. Eligibility will be determined by any member of the study team under direction of the PI and in collaboration with the attending physician through review of inclusion and exclusion criteria as compared to the patients’ presentation, diagnoses and medical history. Jackson Health System’s medical records within Cerner will be accessed under a waiver of HIPAA authorization (see section 21). After collaboration with the clinical team and initial screening for entry criteria, a member of the study team will approach potential subjects for consent and enrollment.

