**7) Study Endpoints\***

The Primary endpoint is change from baseline in the ISTH DIC Score to Day 9.

The Secondary endpoints include change from baseline D-dimers, Fibrinogen & Prothrombin time, length of hospital stay (days), mortality (%), and Pulmonary function (including Time (days) to mechanical ventilation and/or ECMO Duration (days) of new ventilator or extracorporeal membrane oxygenation (ECMO) use, Change from baseline SOFA and SOFA Respiratory sub-score, Number of venous thromboembolisms, Number of major bleeding events

Subjects discharged prior to completion of intervention would be classified as having a successful outcome. We anticipate that all cause morbidity will occur in 10-20% of the COVID study population, despite standard of care. We anticipate that these patients will be deficient in endogenous AT3.

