**8) Procedures Involved\***

Any member of the study team will discuss potential subjects with the clinical team for appropriate pursuit of informed consent and screening for eligibility.

75 eligible subjects, after consent, will have laboratory blood tests for further screening.

25 of those subjects with endogenous **AT3  $\geq$  100%** will continue with SOC.

50 of those subjects with endogenous **AT3 < 100%** will be will be randomly assigned to begin **SOC plus treatment with exogenous AT3 supplementation or only SOC** treatment. The randomization schedule will be established by a member of the study team that is not involved in the informed consent process.

They will all be followed up for laboratory blood tests, study endpoints and adverse events. If they do not meet entry criteria they will be excluded from the study.

[figure not shown]
Consented subjects will be scored according to The International Society of Thrombosis and Haemostasis Disseminated Intravascular Coagulation scale (ISTH DIC) on study visit days 1, 3, 5, 7, 9 and 11.

The SOFA score will be performed only when the parameter is obtained clinically and monitored for changes in patient status on study visit days 1, 3, 5, 7, 9 and 11. Each organ system is assigned a point value from 0 (normal) to 4 (high degree of dysfunction/failure). It will be calculated on admission and Day 11 using the worst parameters measured during the study visit day. If a parameter is not obtained clinically it will be voided for research purposes.

UM IRB# 20201048

AT3 in COVID-19  
January 24, 2022, Version 6.2

After enrollment and each 48h period (+/- 12 hours) thereafter, blood samples are collected and assayed for routine clinical coagulation and inflammation markers, including AT3 activity, D-Dimer, anti-Xa, fibrinogen, and prothrombin time until Day 11.

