### **Procedures for Reporting Adverse Events**

Adverse events may be spontaneously reported, obtained through non-leading questioning, or noted during examination of a subject. Adverse events will be recorded from the signing of informed consent through the last dose of study drug. Serious adverse events will be recorded from the signing of informed consent through hospital discharge.

At each visit, new AEs are recorded sequentially on the **Adverse Event log**. The AE term will note the diagnosis whenever possible, not the individual signs or symptoms (e.g., myocardial infarction will be recorded rather than chest pain, elevated cardiac enzymes, and abnormal ECT). Also recorded are:

- Start and stop date and time
- Whether or not the event is continuing
- Severity (mild, moderate, severe)
  - Mild: usually transient, requiring no special treatment and generally not interfering with usual daily activities
  - Moderate: usually ameliorated by simple therapeutic maneuvers and impairs usual activities
  - Severe: requires vigorous therapeutic intervention and interrupts usual activities. Hospitalization may or may not be required.

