### Appendix C

The Secondary endpoint measurements:

- a. D-dimer level change from baseline to Day 9 in mcg/mL FEU or DDU,
- b. Fibrinogen level change from baseline to Day 9 in mg/dL
- c. Prothrombin time change from baseline to Day 9 in seconds
- d. Length of hospital stay in days,
- e. Mortality (%) of overall and between groups,
- f. Pulmonary function
  - a. Time (days) to mechanical ventilation and/or
  - b. ECMO Duration (days) or extracorporeal membrane oxygenation (ECMO) use,
- g. SOFA score change from baseline to Day 9 and
- h. SOFA Respiratory sub-score change from baseline to Day 9,
- i. Number of venous thromboembolisms from admission to hospital discharge,
- j. Number of major bleeding events from admission to hospital discharge

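### Minor: VTE and major bleeding are counted from admission, which read literally is before consent, AT3 testing and assignment; both counts should start at assignment.

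*Combined protocol and SAP*

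**What the plan says.** Appendix C, items i and j, gives the two windows: "Number of venous thromboembolisms from admission to hospital discharge" and "Number of major bleeding events from admission to hospital discharge". They are the only Appendix C items worded this way; the laboratory and SOFA changes run from baseline. Section 7 lists "Number of venous thromboembolisms, Number of major bleeding events" with no window.

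The order of events comes from two other sections. Section 5 states "Potential subjects will be recruited as inpatients under the care of an attending". Section 8 states "75 eligible subjects, after consent, will have laboratory blood tests for further screening", and only after the AT3 result are subjects with AT3 below 100% randomised and those at or above 100% continued on standard of care.

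The Appendix B flowsheet collects VTEs and bleeding events in the discharge column and shows no start point. The data list in section 8 asks for number and severity of each, with no onset date. Section 10 (Procedures for Reporting Adverse Events) starts both AE and SAE recording at signed consent.

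**The concern.** A between-group count of VTE or major bleeding should contain only events that the assigned treatment could have influenced. An event between admission and assignment cannot be an effect of AT3, yet the written window admits it.

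The consequence differs by comparison:

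- **Randomised arms (AT3 <100%, 25 vs 25).** Pre-assignment events are balanced in expectation. They cause no systematic bias, but they add variance and dilute ratio measures.
- **Comparison with the AT3 ≥100% group.** Randomisation gives no protection here. A thrombosis or bleed before the AT3 test might itself have influenced the AT3 level, so the direction of cause and effect becomes unclear. The trial's hypothesis (section 1) is an association between deficient AT3 and a prothrombotic state, so this ordering matters.

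Major bleeding is also a safety outcome for a drug with anticoagulant action, and section 12 pauses the study for any such event.

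**Working it through.** **Plan's own figure.** There is none to reproduce: no sample-size or power figure depends on this window.

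**Order of events.** Admission (section 5) → consent (sections 5 and 8) → AT3 test (section 8) → assignment (section 8). The counts open at the first step.

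**Do other provisions remove earlier events?**
- Exclusion h in section 3 covers "Ongoing massive surgical or unexplained bleeding"; a bleed that has resolved is outside it.
- Exclusion i covers a history of bleeding or clotting disorder. It does not clearly cover a VTE earlier in the same stay.
- No section limits the counts to new events.

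**Can earlier events be separated afterwards?** Partly. The AE log holds "Start and stop date and time" from consent onward, and Appendix B takes medical and surgical history on Day 1. However, the VTE and bleeding items carry no onset date, and after the last dose only serious events are logged (Appendix B, footnote 2).

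**Illustration for VTE.** From the documents: 25 per randomised arm (section 4). Assumed: post-assignment risk 0.20 on standard of care and 0.10 on AT3, the same pre-assignment risk *p* in both arms, and pre- and post-assignment events independent.

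- Risk counted from admission = 1 − (1 − *p*)(1 − post). At *p* = 0.10: 1 − 0.90 × 0.80 = 0.280 and 1 − 0.90 × 0.90 = 0.190.
- Expected count = 25 × (*p* + post).
- SD of the count difference = √(25 × [2*p*(1 − *p*) + 0.20 × 0.80 + 0.10 × 0.90]).
- Chance gap = probability that two independent Binomial(25, *p*) counts differ by 2 or more (exact).

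| *p* | Risk, SOC vs AT3 | Risk difference | Risk ratio | Expected counts | Difference | SD | Chance gap ≥2 |
|---|---|---|---|---|---|---|---|
| 0 | 0.200 vs 0.100 | 0.100 | 0.50 | 5.0 vs 2.5 | 2.5 | 2.50 | – |
| 2% | 0.216 vs 0.118 | 0.098 | 0.55 | 5.5 vs 3.0 | 2.5 | 2.69 | 0.115 |
| 5% | 0.240 vs 0.145 | 0.095 | 0.60 | 6.25 vs 3.75 | 2.5 | 2.94 | 0.308 |
| 10% | 0.280 vs 0.190 | 0.090 | 0.68 | 7.5 vs 5.0 | 2.5 | 3.28 | 0.470 |
| 15% | 0.320 vs 0.235 | 0.085 | 0.73 | 8.75 vs 6.25 | 2.5 | 3.55 | 0.548 |

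The row *p* = 0 is the count from assignment.

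**Lower-rate case.** Hold the total standard-of-care rate at 20%. This is the 15% deep vein thrombosis plus 5% thromboembolism in the 40-patient series in section 2, assuming no overlap and leaving out catheter-related thrombosis. Assume AT3 halves only the post-assignment part.

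| Pre-assignment part | Counts from admission | Ratio | Counts from assignment | Ratio | Difference, either window |
|---|---|---|---|---|---|
| 2% | 5.0 vs 2.75 | 0.55 | 4.5 vs 2.25 | 0.50 | 2.25 |
| 5% | 5.0 vs 3.125 | 0.625 | 3.75 vs 1.875 | 0.50 | 1.875 |
| 10% | 5.0 vs 3.75 | 0.75 | 2.5 vs 1.25 | 0.50 | 1.25 |

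**Against sampling error.** The approximate 95% interval for the risk ratio is RR × exp(±1.96 × √[(1 − a)/(25a) + (1 − b)/(25b)]), where a and b are the standard-of-care and AT3 risks. From assignment (0.20, 0.10) it is 0.12 to 2.05. From admission at *p* = 10% (0.28, 0.19) it is 0.24 to 1.89. The shift in the ratio is small beside either interval.

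**The case against.** The strongest objection is that admission may simply mean study Day 1. For SOFA, section 8 says "It will be calculated on admission and Day 11 using the worst parameters measured during the study visit day", and Appendix B places that score at Enrollment - Day 1. If items i and j use the word in the same way, little remains beyond a possible same-day gap before assignment. This reading is possible, but nothing states it for these two items, and paired with hospital discharge the word reads naturally as the start of the stay. Two abstractors could count differently.

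Other objections:

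- **Small effect.** The expected count difference does not move, and the comparison is imprecise under either window: expected difference over SD is 2.5/2.50 = 1.00 from assignment and 2.5/3.55 = 0.70 in the worst case above. This stands, and it is why the point is minor.
- **Entry and withdrawal rules.** Exclusion n gives the study team discretion, and section 11 treats bleeding or clotting conditions as ones that can develop during the study. This narrows the problem but does not reliably remove an earlier VTE or resolved bleed.
- **Recoverable data.** Outcomes come from the medical record, so onset can often be found. True, but the plan does not ask for it.
- **High assumed rates.** The main illustration implies total standard-of-care rates (*p* + 0.20) of 22% to 35%, above the 20% taken from section 2. The lower-rate case answers this. Major bleeding has no rate in the documents, so no figure is given for it.
- **No planned analysis affected.** Section 9 compares fastest with slowest recoverers and specifies no arm comparison for these endpoints. This also stands. Appendix C nevertheless fixes what is counted, whichever comparison is made.
- **Consent as an alternative start.** It would match the SAE window and remove most of the problem, but it still precedes the AT3 result and assignment.

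**Conclusion.** The concern holds as a minor point on two secondary endpoints. Followed as written, the window puts events that AT3 could not affect into one efficacy count and one safety count, and it lets events precede the AT3 value that defines the non-randomised group. Between the randomised arms the cost is noise and a diluted ratio. The expected difference in counts is unchanged and the risk difference barely moves (0.100 to between 0.098 and 0.085). These sizes rest on assumed event rates, because the documents give neither a pre-assignment rate nor the interval from admission to consent. If the investigators meant Day 1 by admission, the change only needs to say so. The primary endpoint is unaffected.

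**What to change.** In Appendix C, items i and j, count new events from randomisation to hospital discharge. For the AT3 ≥100% group, start at group assignment on the Day 1 AT3 result. Use the same window in section 7. Record an onset date with each VTE and bleeding event, taking it from the AE log where one exists, and enter earlier events of the same stay under the Day 1 medical and surgical history. Admission-based counts can still be reported descriptively. It would also help to state in section 8 whether admission means Enrollment - Day 1 for SOFA.

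The cost is two phrases in Appendix C, a matching window in section 7 and one date per event. The downside is fewer counted events. Under the main assumptions, the two randomised arms together would have 25 × (0.20 + 0.10) = 7.5 expected VTEs, instead of 8.5, 10.0, 12.5 or 15.0 at a pre-assignment risk of 2%, 5%, 10% or 15%. The events lost are those AT3 could not have influenced.

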**Appendix D**

Estimating FiO2			Estimated PaO2 from a given SpO2		Modified GCS	
Method	O2 flow (l/min)	~FiO2 (%)	SpO2 (%)	PaO2 (mmHg)		
Nasal cannula	1	24	80	44	Eyes	4 = spontaneously
	2	27	81	45		3 = to verbal
	3	30	82	46		2 = to painful stimuli
	4	33	83	47		1 = no response
	5	36	84	49		6 = to verbal command
	6	40	85	50		5 = localized to pain
Nasopharyngeal catheter			86	52	Motor	4 = withdraws to pain
	4	40	87	53		3 = decorticate, arms flex
	5	50	88	55		2 = decerebrate, arms ext
Face mask			89	57	Verbal	1 = no response
	5	40	90	60		5 = oriented, converses
	6-7	50	91	62		4 = disoriented & talks
Face mask with reservoir			92	65	No ETT	3 = inappropriate words
	7-8	60	93	69		2 = incomprehensible words
			94	73		1 = no response
	6	60	95	79		5 = seems able to talk
	7	70	96	86		3 = questionable ability to talk
	8	80	97	96	Verbal w/ETT	1 = generally unresponsive
	9	90	98	112		
	10	95	99	145
